# SPECIFIC AIMS

#### OBJECTIVE

The primary objective of this Phase 2 trial is to compare the change from baseline to week 8 of the peptide intranasal oxytocin (IN-OXT) on changes in hyperphagia using the Hyperphagia Questionnaire-Clinical Trials (HQ-CT) in children and adolescents with PWS. We have obtained an IND for the use of IN-OXT for PWS (IND 121109) and have acquired both the IN-OXT and matching placebo (Manufactured by Novartis as Syntocinon - see letter and COA of Batch in appendix). We will also compare the effects of IN-OXT from baseline to week-8 on repetitive behaviors (RBS-R), weight, BMI and body composition, quality of life (WHOQOL, Caregiver Strain Questionnaire), salivary oxytocin concentration, and safety measures. Safety will be assessed with routine laboratory monitoring, physical exam, urine pregnancy test for menstruating females, and collection of vital signs. The Aberrant Behavior Checklist (ABC) will also be used as a safety measure for both suicidality (per FDA guidelines) and for adverse events (aggression/temper tantrums). This Phase 2 study is designed to generate preliminary data for future Phase 3 trials, and targets symptoms in this population that currently have no effective treatments. By treating these symptoms earlier in life in a pediatric PWS population we may maximize the treatment impact. This study supports the Orphan Product Divisions goal of identifying and promoting the development of treatments indicated for rare diseases or conditions. Our proposed treatment will target hyperphagia in subjects with PWS, a symptom for which there is currently no effective treatment.

This study will provide essential data that is needed for drug development and eventually drug approval.

We propose a three-year randomized, double-blind, placebo-controlled 8-week treatment trial of IN-OXT 16 IU/day in 50 subjects aged 5 to 17 years with PWS. To allow for dose optimization, we allow one downward titration to 12 IU if adverse events occur, and one upward titration to 24 IU at week 2 for lack of response on hyperphagia.

**Primary:** To compare IN-OXT vs. placebo on changes on the Hyperphagia Questionnaire-Clinical Trials (HQ-CT) from baseline to week 8 in children with PWS. We hypothesize that IN-OXT will be significantly superior to placebo in improving hyperphagia.

Secondary: To compare the change from baseline to week-8 of IN-OXT vs. placebo on:

- 1. Repetitive Behavior Scale-Revised (RBS-R).
  - We hypothesize that IN-OXT will significantly reduce repetitive behaviors from baseline to endpoint as measured by a reduction of the score on the RBS-R when compared to placebo.
  - We hypothesize that IN-OXT will significantly reduce rigid behaviors from baseline to endpoint as measured by a reduction of the score on the MERS-PWS when compared to placebo.
- 2. Weight, BMI (z-score) and Body composition via bioelectrical impedance analysis
  - We hypothesize that IN-OXT will significantly reduce weight and BMI compared to placebo.
- 3. We hypothesize that IN-OXT will significantly reduce body fat compared to placebo, as measured by body composition via bioelectrical impedance analysis
- 4. Quality of Life Measures
  - World Health Organization Quality of Life Questionnaire (WHOQOL)
    - We hypothesize that IN-OXT will improve quality of life measured by an increase in overall score on the WHOQOL from baseline to endpoint when compared to placebo.

- Caregiver Strain Questionnaire (CSQ)
  - We hypothesize that IN-OXT will improve quality of life measured by a reduction in overall score on the CSQ from baseline to endpoint when compared to placebo.
- 5. Salivary Oxytocin Concentration
  - We hypothesize that higher concentrations of salivary oxytocin will be correlated with positive changes on each outcome measure, indicating improvement in symptoms.
- 6. Safety Analyses
  - We hypothesize that IN-OXT will not increase side-effect burden from baseline to endpoint compared to placebo.

#### **Exploratory:**

- 1. To compare IN-OXT vs. placebo on changes in dietary intake using the ASA 24: Automated, Self- Administered, 24 hour Recall diet diary system, as provided by the National Cancer Institute (NCI).
- 2. To examine the impact of medical co-morbidities on treatment outcome.
- 3. To examine the relationship between weight-based dosing and treatment response on hyperphagia.
- 4. To compare IN-OXT vs. placebo on changes in hormone levels at baseline and endpoint. Measured hormones will include ghrelin, pancreatic polypeptide, peptide YY, GLP-1, insulin, glucagon, testosterone and estrogen. We will also look at changes in HbA1C.

# Phase 2 Study: Intranasal Oxytocin vs. Placebo for the Treatment of Hyperphagia in Children and Adolescents with Prader-Willi Syndrome

### [IND 121109 acknowledged 8/27/14]

#### **BACKGROUND AND SIGNIFICANCE**

Prader-Willi Syndrome (PWS) has been designated as a rare disease by the National Institutes of Health and is categorized as such with the NIH Office of Rare Diseases Research. [1]. Inclusion on this list requires a prevalence of less than 200,000 people in the United States. According to the Prader-Willi Syndrome Association USA and a review of the literature, current estimates of the prevalence of PWS range from 1: 8,000 - 1: 30,000 with the most likely prevalence falling around 1 : 15,000 individuals [2-8]. Based on current U.S. Census data there are 317,434,622 people living in the U.S. Using the above prevalence estimates, the prevalence of PWS ranges from 10,581 to 39,679, and the most likely prevalence is approximately 21,000 Americans [9]. Using the most current available data from the U.S. Census (2010), there are 74,181,467 people in the pediatric population in the US (age < 18 vears) [10]. Assuming that the prevalence of PWS falls between 1: 8.000 and 1: 30.000, there are currently between 2,473 and 9,273 people under age 18 with PWS. PWS is a rare neurodevelopmental disorder caused by lack of expression of paternally derived imprinted material on chromosome 15g11-g13. Maternal duplications and triplications of the 15g11-g13 region also account for the most frequently observed autosomal abnormalities in idiopathic ASD [11 – 19]. PWS is characterized by mild to moderate intellectual disabilities, repetitive/compulsive behaviors and rigidity, social cognition deficits and severe hypotonia at birth, followed by the onset of hyperphagia later in life.

This study supports the Orphan Product Divisions goal of identifying and promoting the development of treatments indicated for a rare disease or condition. The proposed product is intranasal oxytocin (IN-OXT) (Syntocinon, manufactured by Novartis). The batch certificate of analysis for the product lot manufactured on 9/13/2014 and having an expiration date of 2017 has been submitted to the IND; see letter in appendix). This proposal aims to target symptoms of PWS for which treatment options do not currently exist, and will provide essential data that is needed for product development and eventually product approval. In this Phase 2 trial of IN-OXT we will evaluate the effectiveness of the product for individuals with PWS and determine the common short-term side effects and risks associated with the treatment. We have submitted this protocol to FDA and have received IND 121109. All required documents are on file with the FDA and are included in the appendix of this proposal, including the Certificates of Analysis for both drug and placebo, the product insert and the Container Label Statement.

We propose a three-year randomized, double-blind, placebo-controlled 8-week treatment trial of IN-OXT 16 IU/day in 50 subjects aged 5 to 17 years with PWS. A recent 1 week crossover trial by [name] (a consultant on this proposal) using this dose of IN-OXT in PWS demonstrated improvement in hyperphagia, and we discuss her results, as well as our pilot data with this dose below. To allow for optimization, we allow one downward titration to 12 IU if adverse events occur, and one upward titration to 24 IU at week 2 for lack of response on hyperphagia.

We will determine if IN-OXT is effective in improving hyperphagia in PWS as measured by changes on the Hyperphagia Questionnaire-Clinical Trials (HQ-CT). We will also examine secondary outcomes of changes in repetitive behaviors (i.e. skin picking and nail-biting that co-occur with hyperphagia) using the reliable and valid Repetitive Behavior Scale-Revised (RBS-R). We will also measure weight, BMI (z-score) and body composition (via bioelectrical

impedance analysis), guality of life, salivary oxytocin concentration, and safety measures in patients with PWS. PWS has well-known genetic targets and documented structural and functional lesions of the OXT neurons of the PVN. PWS is a unique and relatively genetically homogenous syndrome. Furthermore, IN-OXT has a favorable side effect profile and will target core symptoms for which there are no effective available treatments. Previous studies of IN-OXT treatment for PWS had several limitations in study design which our group has improved upon, as noted above. Based on [name]'s positive short-term trial of IN-OXT for the treatment of hyperphagia in PWS, we have opted to use a dose of 16 IU/day. Her study yielded weight based dosing of 0.2 IU/lb - 0.4 IU/lb. One patient who was underweight (32 lb) had a 0.5 IU/Ib weight based dose and experienced temper tantrums. Thus we will not enroll subjects who weigh less than 40lb in order to maintain weight based dosing below 0.4 lb/IU. It is hypothesized that lower doses of IN-OXT may reduce binding to vasopressin receptors, and decrease the risk of the temper tantrum side effect observed in other trials. This is consistent with a recent single-dose crossover trial of IN-OXT in healthy controls with a modified nasal delivery device demonstrated that plasma OXT levels were similar in low-dose and high-dose IN OXT groups and both were greater than in the placebo group, but that the low dose IN-OXT was superior to the high dose IN OXT and to placebo in reducing anger ratings in response to emotionally ambiguous faces [101]. As the two existing trials of IN-OXT in PWS have enrolled both males and females, and the hyperphagia symptoms of PWS are not sexually dimorphic, we intend to enroll both sexes in equal numbers. IN-OXT has been used safely in multiple human studies involving men and women and is well tolerated in both adult and pediatric PWS populations and we expect a similar safety profile in our proposed study.

In selecting an orphan population, PWS, with a known specific genetic locus, and in selecting a treatment, IN- OXT, that specifically matches the underlying deficit in the structure and function of OXT neurons in PWS, we expect that this study will have substantially greater power to detect significant drug vs placebo differences.

**Hyperphagia and Obesity in Prader-Willi Syndrome:** Behavioral and fMRI studies have demonstrated that compulsive eating in PWS is due to decreased satiety rather than increased hunger. The characteristic behavioral pattern of PWS begins around age four in tandem with the onset of hyperphagia and is characterized by obsession with food, temper tantrums, stubbornness, controlling and manipulating behavior, compulsive behaviors and difficulty with changes in routine [4, 22]. These behavioral problems are the most challenging problems in PWS and greatly impact the quality of life of individuals with PWS and their families [23 – 25].

Several studies have determined that the eating behaviors observed in PWS are due to decreased satiety rather than increased hunger [33, 34]. Functional magnetic resonance imaging data has revealed that after eating a meal, PWS subjects display hyperfunctionality in the limbic and paralimbic reward regions (amygdala, NAc) that drive eating behavior, and in regions that suppress food intake such as the medial prefrontal cortex. They also had lower activity in the hypothalamus and hippocampus in response to food [38, 39]. These results further implicate the failure of satiety that is observed in PWS and suggest an abnormal food motivation phenotype that involves hyperactivation of the subcortical reward circuitry and hypoactivation in cortical inhibitory regions resulting in compulsive eating. Obesity secondary to the disordered eating behaviors that characterize the PWS phenotype also contributes to the increased morbidity and mortality of the syndrome.

Obesity-related cardiovascular complications and sleep apnea are among the most common causes of death in adults with PWS. Additionally, diabetes mellitus secondary to disordered eating and obesity is common [27]. The mortality rate in PWS is up to six times higher than in

IQ matched controls, with obesity being the main factor [28].

There is conflicting evidence relating to the levels of hormones responsible for feelings of satiety and hunger in PWS. Comparisons of PWS patients to BMI and adiposity-matched obese patients demonstrated similar responses of gut hormones fasting and post-prandial, aside from overall increased levels of ghrelin [36]. It is believed that the increased levels of ghrelin could be responsible for increased hunger, despite high levels of postprandial satiety in PWS patients. Other studies have demonstrated increased leptin levels, and decreased fasting pancreatic polypeptide levels in PWS patients compared to BMI matched patients [37]. More recently, ghrelin concentrations were measured across nutritional phases in a 12-year longitudinal study of individuals with PWS (5 weeks old to 21 years old), individuals with early onset obesity of unknown origin and non-obese sibling controls. They concluded that ghrelin concentrations are significantly higher in early nutritional phases of PWS long before the onset of hyperphagia and especially during phases of poor appetite and feeding. Thus it is possible that high ghrelin concentrations do not contribute to the hyperphagic nutritional switch seen in PWS [102].

Clearly there are multiple neuropeptide and neurotransmitter mechanisms that can contribute to obesity and the onset of hyperphagia in PWS. In order to collect more information about these mechanisms we will measure ghrelin concentrations, as well as pancreatic polypeptide, peptide YY, GLP-1, insulin, glucagon, testosterone and estrogen, and HbA1C at baseline and endpoint to observe potential effects of IN-OXT treatment as it relates to both hyperphagia and the concentration of ghrelin and these other measures.

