**Research Strategy And Feasibility:** We propose a three year, phase 2, randomized doubleblinded 8-week treatment trial of IN-OXT vs. placebo in 50 child and adolescent subjects (25 male and 25 female) aged 5 to 17 years with a diagnosis of PWS. PWS diagnosis will be confirmed by study team via patient interview and confirmation by patient's past medical records and genetic testing results. At the screening visit, patient will have the opportunity to learn about the study and seek clarification on any outstanding questions. If patient voluntarily agree to participate, study team will work with the patients to complete the informed consent and if applicable, assent. In addition, a psychiatric interview and medical history review will be conducted to screen the patient for eligibility. The study team will also review patient's concomitant medications, assess for patient condition with CGI-S and hyperphagia using the Hyperphagia Questionnaire-Clinical Trials (HQ-CT). If patient meets selection criteria, the study team will arrange on behalf of the patient for an out-patient Quest visit, at which time patient will be asked for a screening blood draw to provide information on CBC, BMP, LFT, IGF-1, thyroid panel, lipid panel, testosterone, estrogen, hemoglobin A1C, and for applicable patient, a urine pregnancy test. Once the screening blood work results are available and all results are within acceptable range, and patient is otherwise eligible, patient will be invited for an in person visit to clinic where additional assessments including a complete physical and neurological exam, intelligence test, interval health or medication change, and if applicable, repeat urine pregnancy test will be conducted. If patient continues to meet all study inclusion and exclusion criteria and agrees to continue with study participation, the study team will formally submit the patient for randomization. The randomization is done in a 1:1 placebo to oxytocin ratio and stratified for gender. The result is blinded to the study team and the process is performed by the study pharmacist at the Clinical Research Pharmacy using a computer generated randomization table. Patients will receive a supply of oxytocin spray bottle with each spray dispensing 4 IU, or a matching placebo. The participant will start with an initial dose of 2 sprays per nostril (4 sprays per day), or 16 IU/day IN-OXT or placebo. To allow for optimization for adverse events or lack of response, we allow for one downward titration to 12 IU (3 sprays per day), and one upward titration to 24 IU (6 sprays per day) at week 2. This will also allow us to examine the relationship between weight based dosing and treatment response. Syntocinon (synthetic intranasal oxytocin) and matched placebo made by Novartis will be used in this protocol. We have an IND for the use of IN-OXT in PWS (IND 121109).

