#### Titration Schedule:

Adverse events: Study physician will review with study participants regarding the nature,

duration and severity of noted adverse events. The study physician will make clinical judgements on the relationship between reported adverse events with study medication. If there is a high likelihood of adverse events being related drug effects, the subject will titrate down from 16 IU/day (4 sprays per day) to 12 IU/day (3 sprays per day) and will be reassessed in one week). At the next assessment the side effects and tolerability will again be reviewed by the PI and medical monitor. If the side effects have resolved, the subject will be titrated back up to 16 IU/day. If the side effects persist, the subject may continue on the 12 IU/day for another week; or will be discontinued from the study at the judgement of the PI. Subjects who do not receive the full dose by week four will be discontinued. Any subject who is discontinued from the study will be referred for continued medical follow up.

Lack of response: One upward titration will be allowed at week 2 to 24 IU/day (4 sprays per day) if study clinician, with consultation of the PI, determines that study subject experiences no response on hyperphagia via a categorical yes/no determination, and has no adverse events. In our current ongoing pilot study, and in [name]'s study, the initial hyperphagia response was observed at the week 1 and week 2 ratings.

**Instructions for Dosing:** Once the cap has been removed from the spray, the device should be held upright to the nostril and the actuator depressed. The patient should be in the sitting position and should be instructed to inhale gently through the nose while the actuator is being depressed. The head should be tilted back once the actuator is depressed to ensure that no fluid runs out of the nose. Parents may assist the child with dosing.

**Outcome Measures:** Project outcomes will be determined by changes in scores of parent and clinician rated measures from baseline to week 8 and comparisons of week 8 measures between active treatment and placebo groups. Assessments will be administered according to the schedule of events in **Table 2**.

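### The Titration Schedule prints the 24 IU/day step as 4 sprays, which deliver only 16 IU; separately, the 0.4 IU/lb figure behind the 40-lb limit does not hold at 24 IU/day

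*Combined protocol and SAP*

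**What the plan says.** **Spray count.** Research Strategy And Feasibility gives 4 IU per spray, a starting dose of 4 sprays for 16 IU/day, and "one upward titration to 24 IU (6 sprays per day) at week 2". The adverse-event paragraph of the Titration Schedule agrees on the starting dose: "the subject will titrate down from 16 IU/day (4 sprays per day) to 12 IU/day (3 sprays per day"). The lack-of-response paragraph that follows reads "One upward titration will be allowed at week 2 to 24 IU/day (4 sprays per day"). The step is open to a child when the study clinician, consulting the PI, "determines that study subject experiences no response on hyperphagia via a categorical yes/no determination, and has no adverse events". Neither place sets a weight condition.

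**Weight-based dose.** Background and Significance states that "we have opted to use a dose of 16 IU/day", following an earlier short crossover trial in children with PWS. It adds "Her study yielded weight based dosing of 0.2 IU/lb - 0.4 IU/lb" and "One patient who was underweight (32 lb) had a 0.5 IU/Ib weight based dose and experienced temper tantrums". It then concludes: "Thus we will not enroll subjects who weigh less than 40lb in order to maintain weight based dosing below 0.4 lb/IU". Exclusion Criteria, item 3, applies the 40-lb limit. The 24 IU step appears in Specific Aims, Background and Significance, Research Strategy And Feasibility and the Titration Schedule. No section gives the IU/lb that results from it.

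**The concern.** The spray count is the instruction a family acts on. The Titration Schedule is where staff would look up the step, and there the IU figure and the spray figure disagree. If the spray figure is followed, a non-responder stays on the starting dose. The treatment then delivered is a 16 IU/day regimen without the intended optimisation. The comparison by randomised arm remains valid, but it describes a lower-dose regimen than the one planned. In the exploratory work on weight-based dosing (Exploratory aim 3; Additional Analyses, item 5), a child coded at 24 IU who took 16 IU would carry the wrong exposure.

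The 0.4 IU/lb figure is a smaller matter of the same kind. The text gives a tolerability reason for the 40-lb limit and names a dose level that the limit is meant to secure. That level is not secured at the highest dose the protocol allows.

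**Working it through.** **Inputs.** 4 IU per spray; 4 sprays at the start; 6 sprays for 24 IU (Research Strategy And Feasibility). 4 sprays printed for 24 IU (Titration Schedule). 40-lb limit (Exclusion Criteria, item 3). 0.2 to 0.4 IU/lb, and a 32-lb child at 0.5 IU/lb (Background and Significance). Permitted doses of 12, 16 and 24 IU/day.

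**Spray count.** Dose = sprays × 4 IU.

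- 3 × 4 = 12 IU and 4 × 4 = 16 IU, as the plan states.
- 6 × 4 = 24 IU, as in Research Strategy And Feasibility.
- The printed step gives 4 × 4 = 16 IU, so there is no increase.
- If 16 IU is recorded as 24 IU, IU/lb is overstated by 24/16 = 1.5, or 50%, at any weight.
- From week 2 to week 8 is 42 days. The printed count gives 42 × 4 = 168 sprays and the intended count 42 × 6 = 252. The difference is 84 sprays × 4 IU = 336 IU. This applies only to an active-arm child with full compliance from day 14 to day 56; a placebo child loses no oxytocin.

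**Weight-based dose.** IU/lb = daily dose / weight. The plan's own figures are reproduced first:

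- 16/32 = 0.50, the cited child.
- 16/40 = 0.40, the stated figure at the weight limit. A child of exactly 40 lb is eligible, so this is at 0.4, not below it.
- 16/0.4 = 40 lb and 16/0.2 = 80 lb, so at this dose the earlier trial's range corresponds to 40 to 80 lb.

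For the permitted doses:

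| Daily dose | IU/lb at 40 lb | Weight giving 0.5 IU/lb | Weight giving 0.4 IU/lb |
|---|---|---|---|
| 12 IU | 0.30 | 24 lb | 30 lb |
| 16 IU | 0.40 | 32 lb | 40 lb |
| 24 IU | 0.60 | 48 lb | 60 lb |

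At 12 and 16 IU/day every eligible child is at or below 0.4 IU/lb. At 24 IU/day, active-arm children from 40 lb to under 60 lb exceed 0.4, and those from 40 lb to under 48 lb exceed 0.5. The highest value is 0.60/0.40 = 1.5 times the stated figure.

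**The case against.** **On the spray count.** The misprint partly reveals itself, because a child already on 4 sprays cannot be titrated up to 4. The IU dose is printed correctly throughout, and Research Strategy And Feasibility has the right count. Under Adverse Event Reporting and Measures of Compliance, bottles are weighed before and after dispensing, and the pharmacist alerts the team to non-compliance. All of this stands and makes an undetected error less likely. It is not full protection, since a pharmacist working from the Titration Schedule would also expect 4 sprays. A reader might infer that every up-titrated child would be 336 IU short. The documents do not support that, given the 1:1 placebo randomisation and these checks.

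**On the 0.4 IU/lb figure.** The sentence follows the choice of 16 IU/day and is most naturally a starting-dose rationale. The 40-lb limit and the 24 IU step are both disclosed, so 0.60 is a single division away. That stands too. A reader might infer that 0.4 IU/lb is a trial-wide ceiling which the 24 IU step breaches, so that the step needs a minimum weight. Neither the eligibility criteria nor the titration rules make it a ceiling. Research Strategy And Feasibility also gives study of weight-based dosing as one use of the titration. A weight condition would narrow that range and tie dose to weight, which is a trade-off for the sponsor and not a correction.

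**On safety.** A reader might also infer that 24 IU/day is unsafe in lighter children. The 0.5 IU/lb signal is one underweight child. The step requires no adverse events at 16 IU. The ABC is completed at every visit, and the medical monitor reviews side effects after each one. In the earlier 18-week crossover trial, the rise in tantrums was at 32 and 40 IU twice daily (64 and 80 IU/day). None is reported for its lower doses of 18 and 24 IU twice daily (36 and 48 IU/day). Those subjects were aged 12 to 30 and no weights are given, so that trial neither supports nor rules out a concern at 0.60 IU/lb.

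**Conclusion.** Both points hold, and both should be fixed. The first matters more: the operative dosing section prints a spray count that delivers 16 IU where 24 IU is meant, and it conflicts with its own preceding paragraph and with Research Strategy And Feasibility. The consequence is conditional on that section being followed. If it is, non-responders get no increase, and the exploratory IU/lb value for an affected active-arm child could be overstated by 50%.

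The second is a clarification. The 0.4 IU/lb statement holds, as at or below, only for 16 IU/day or less. The permitted maximum is 0.60 IU/lb, and no section says so. This reading takes the printed lb/IU as IU/lb, which the surrounding figures require.

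The number of children affected by either point cannot be computed, because the documents give no weight distribution and no expected rate of up-titration. The evidence shows a text that misstates the dose. It does not show an unsafe dose or a breached dosing rule.

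**What to change.** 1. In the lack-of-response paragraph of the Titration Schedule, change 4 sprays to 6 sprays for 24 IU/day, and check that dispensing and family instructions carry the same count.
2. In Background and Significance, correct the unit and reword the end of the sentence along these lines: *at or below 0.4 IU/lb at the 16 IU/day starting dose; the maximum after up-titration to 24 IU/day is about 0.60 IU/lb (24 IU at 40 lb)*.
3. State the same maximum in the Risks text, which now mentions tantrums at higher doses without any IU/lb figure.

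The cost is three text edits. Dosing design, eligibility, sample size, visits and assessments do not change. The downside is that the protocol would then openly permit more than the 0.5 IU/lb it cites as the reason for the weight limit, and the sponsor should be ready to explain that.
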